6.1.4.2. Tipping Point Analysis

As a sensitivity analysis to the multiple imputation analysis as described in Section 6.1.4.1 for the S-IGA primary endpoint, a tipping point analysis will be performed in order to determine the inflection point at which the inference under the MNAR assumption changes substantially. This will be used to check the robustness of the imputation.

The sensitivity analysis will be performed by using a specified sequence of shift parameters, which will adjust the imputed values for observations in the active treatment group. The range of shift parameters to be included in this analysis are -1.5 to 1.5 by 0.2. Once the likely point of the shift is determined, the analysis will be rerun using an expanded range around the suspected tipping point, with greater precision (i.e., to 2 decimal places, by 0.01). Thus, the value at which the results of the analysis are shifted from significant (i.e., $\alpha \leq 0.05$) to non-significant (i.e., $\alpha > 0.05$) will be determined.

Step 1 of the analysis will be the same as for the multiple imputation analysis as described in Section 6.1.4.1. However, Step 2 of the analysis is where the shift parameters will be applied. Step 3 will be similar to the multiple imputation analysis described in Section 6.1.4.1, however, the BY statement in PROC FREQ will also include the shift parameter (i.e., by <shift parameter> <imputation number> <shift parameter> <visit>); this will also be included in the PROC MIANALYZE steps. Pseudo-code for Step 2 is as follows:

```
proc mi data=example_1 seed=51192215 nimpute=XX out=example_2;
  class <treatment> <country> ;
  monotone regpmm(<baseline score> ..... <visit8 score>);
  var <treatment> <country> <baseline score> ..... <visit8 score>;
  mnar adjust( <visit2 score> / shift=YY adjustobs=(treatment = 'Vehicle') );
  mnar adjust( <visit4 score> / shift=YY adjustobs=(treatment = 'Vehicle') );
  mnar adjust( <visit8 score> / shift=YY adjustobs=(treatment = 'Vehicle') );
run;
```

XX will be the determined based on the proportion of missing data across visits. YY will encompass the range of shift parameters as pre-specified above.

6.1.5. Analysis Visit Windows

Visits will be analyzed as scheduled. Unscheduled, early termination, and/or repeated measurements will only be included if a scheduled measurement is not available and the unscheduled, early termination, or repeated measurement falls within the analysis visit windows as described in Table 2. The windows follow the Schedule of Events in Table 1. Unscheduled/repeated measurements will be listed.

Table 2: Analysis Visit Windows

Visit Name	Visit Number	Target Start Day	Lower Limit	Upper Limit
Week 2	3	14	2	22
Week 4	4	28	23	42

Visit Name	Visit Number	Target Start Day	Lower Limit	Upper Limit
Week 8	5	56	43	61
Week 9	6	63	62	--

6.1.6. Pooling of Sites

Not applicable.

6.1.7. Derived Variables

- **S-IGA success** = S-IGA of “Clear” or “Almost Clear” plus a 2-grade improvement from baseline.
- **B-IGA success** = B-IGA of “Clear” or “Almost Clear” plus a 2-grade improvement from baseline.
- **SI-NRS 4-point reduction** = achievement of a 4-point reduction in SI-NRS pruritus score at Weeks 2, 4, and 8 compared to baseline, calculated only for subjects with an SI-NRS pruritus score of ≥ 4 at baseline.
- **WI-NRS 4-point reduction** = achievement of a 4-point reduction in WI-NRS pruritus score at Weeks 2, 4, and 8 compared to baseline, calculated only for subjects with a WI-NRS pruritus score of ≥ 4 at baseline.
- **PSSI** = (erythema score + induration + desquamation) \times extent of scalp affected (range 0 to 72). Erythema, induration, and desquamation are scored on a scale of 0 to 4, where 0 = absent and 4 = severest possible; extent of scale affected is scored on a scale of 0 to 6, where 0 = 0% of involved area and 6 = 90-100% of involved area.
- **PSSI-50** = achievement of a 50% reduction in PSSI from baseline
- **PSSI-75** = achievement of a 75% reduction in PSSI from baseline
- **PSSI-90** = achievement of a 90% reduction in PSSI from baseline
- **PSSI-100** = achievement of a 100% reduction in PSSI from baseline
- **Time to PSSI-50 (days)** = date of first PSSI-50 achievement – Day 1 date + 1. Subjects not achieving PSSI-50 will be censored at day of study discontinuation or date lost to follow-up, whichever is later. Due COVID-19-related site closures, some discontinuation visits occurred much later than Week 9, so time to PSSI-50 may be after Week 9.
- **Time to PSSI-75 (days)** = date of first PSSI-75 achievement – Day 1 date + 1. Subjects not achieving PSSI-75 will be censored at day of study discontinuation or date lost to follow-up, whichever is later. Due COVID-19-related site closures, some discontinuation visits occurred much later than Week 9, so time to PSSI-75 may be after Week 9.

- **Time to PSSI-90 (days)** = date of first PSSI-90 achievement – Day 1 date + 1. Subjects not achieving PSSI-90 will be censored at day of study discontinuation or date lost to follow-up, whichever is later. Due COVID-19-related site closures, some discontinuation visits occurred much later than Week 9, so time to PSSI-90 may be after Week 9.
- **PASI** = $(0.1 \times [E_h + T_h + S_h] \times A_h) + (0.2 \times [E_a + T_a + S_a] \times A_a) + (0.3 \times [E_t + T_t + S_t] \times A_t) + (0.4 \times [E_l + T_l + S_l] \times A_l)$

where E , T , and S are erythema, thickness, and scaling, respectively, scored on a scale of 0 to 4, A is estimated area of skin involved, graded on a scale of 0 to 6, and h , a , t , and l are head, arms, trunk, and legs, respectively (range for total score 0 to 72). If any of the component scores are missing, the PASI cannot be calculated.

- **PASI-50** = achievement of a 50% reduction in PASI from baseline
- **PASI-75** = achievement of a 75% reduction in PASI from baseline
- **PASI-90** = achievement of a 90% reduction in PASI from baseline
- **Time to PASI-50** = date of first PASI-50 achievement – Day 1 date + 1. Subjects not achieving PASI-50 will be censored at day of study discontinuation or date lost to follow-up, whichever is later. Due COVID-19-related site closures, some discontinuation visits occurred much later than Week 9, so for purposes of this calculation, the upper limit for time to PASI-50 will be capped at Day 68 (Week 9).
- **mPASI** = $(0.1 \times [E_h + T_h + S_h] \times pA_h) + (0.2 \times [E_a + T_a + S_a] \times pA_a) + (0.3 \times [E_t + T_t + S_t] \times pA_t) + (0.4 \times [E_l + T_l + S_l] \times pA_l)$

where E , T , and S are erythema, thickness, and scaling, respectively, scored on a scale of 0 to 4, pA is estimated area of skin involved as an actual percentage (i.e., percentage in the eCRF/10) if the percent involvement is <10% OR as graded on a scale of 0 to 6, and h , a , t , and l are head, arms, trunk, and legs, respectively (range for total score 0 to 72). If any of the component scores are missing, the mPASI cannot be calculated.

- **DLQI Score** = sum of the 10 questions (individual questions scored as Very much=3, A lot=2, A little=1, Not at all=0, with Not relevant recoded to 0; Question 7: Yes=3, No=0, with Not relevant recoded to 0; range for score 0 to 30). If 1 item is missing, that item is scored as 0. If 2 or more items are missing, the score should not be calculated.
- **CDLQI Score** = sum of the 10 questions (individual questions scored as Very much=3, Quite a lot=2, Only a little=1, Not at all=0; Question 7: if the last week was school time, the question was scored as Very much=3, Quite a lot=2, Only a little=1, Not at all=0, with Prevented school recoded to 3, and if the last week was vacation, the standard responses apply; range for score 0 to 30). If 1 item is missing, that item is scored as 0. If 2 or more items are missing, the score should not be calculated.

- **PSD Total score** = sum of the 16 questions (individual questions scored 0 to 10, where higher scores indicate more severe symptoms; range for total score 0 to 160). If 1 or more items are missing, the score is not calculated.
- **Compliance** = number of applications divided by the expected number of IP applications for each subject. Compliance will be calculated using drug accountability data over the entire treatment period for each subject, up to treatment completion or discontinuation.
 - **Number of expected IP applications** = 56 for subjects who complete the study or number of days between first and last application of IP (last treatment date - first treatment date + 1) for subjects who discontinue early from the study.
 - **Number of IP applications** = number of expected IP applications – missed IP applications as collected in the electronic case report form (eCRF).
- **Weight of IP (g)** = returned can weight – dispensed can weight.
- **Body mass index (BMI) (kg/m²)** = [weight (kg) / height (cm) / height (cm)] x 10,000.
- **BMI Categories**
 - Underweight: BMI < 18.5
 - Normal: 18.5 ≤ BMI ≤ 24.9
 - Overweight: 25.0 ≤ BMI ≤ 29.9
 - Obese: BMI ≥ 30.0
- **Change from baseline** = value at current time point – value at baseline.
- **Treatment emergent AE (TEAE)** = any AE with an onset date/time after the first application of IP.
- **PHQ-8** = sum of the 8 questions (individual questions scored as Not at all=0, Several days=1, More than half the days=2, and Nearly every day=3; range for score 0 to 24). If more than 1 item is missing, the score should not be calculated. If 1 item is missing, the score is calculated as (sum of answered items*8)/number of answered items.

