6.1.3. Multiple Comparisons

To control for multiple comparisons among the secondary endpoints, the following testing plan will be used, as outlined in Figure 1.

Upon demonstration of statistical significance for S-IGA Success at Week 8, the secondary endpoint of B-IGA Success at Week 8 will be tested hierarchically at the 5% significance level.

If the test for B-IGA Success at Week 8 is significant, the α of 0.05 will be split to test 2 families of secondary endpoints. The first family comprise the PSSI-75, which will be tested at the $\alpha = 0.03$ level. If the test of PSSI-75 is statistically significant, then $\alpha = 0.03$ will be used with a Holm testing procedure to test the 4 endpoints of time to success in PSSI-50, change from baseline in Total PSD score at Week 8, change from baseline in Total PSD score at Week 4, and PSSI-90 at Week 8. The remaining $\alpha = 0.02$ will be used to test the second family, comprising the SI-NRS at Week 8, the SI-NRS at Week 4, and the SI-NRS at Week 2. The tests within this second family will be hierarchical, beginning with the endpoint at Week 8, followed by Week 4 and Week 2.

Figure 1: Primary and Secondary Endpoint Testing

Achievement of IGA success is a score of “clear” or “almost clear” plus a 2-grade improvement from baseline.
 SI-WRS Success is a 4-point reduction in SI-NRS among subjects with SI-NRS ≥ 4 at baseline.
 B-IGA = Body-Investigator Global Assessment; EP = endpoint; CFB = change from baseline; PSSI = Psoriasis Scalp Severity Index; S-IGA = Scalp-Investigator Global Assessment; SI-NRS = Scalp Itch - Numeric Rating Scale.

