6.1.8. Data Adjustments/Handling/Conventions

All collected data will be presented in Clinical Data Interchange Standards Consortium (CDISC) datasets. Data not subject to analysis according to this plan will not appear in any tables or graphs but will be included only in the CDISC datasets.

All *P* values will be displayed in 4 decimals and rounded using standard scientific notation (e.g., 0.XXXX). If a *P* value less than 0.0001 occurs it will be shown in tables as <0.0001; similarly, if a *P* value greater than 0.9999 occurs it will be shown in tables as >0.9999.

Adverse events will be coded using the Medical Dictionary for Regulatory Activities (MedDRA) version 23.0 thesaurus.

A treatment-related AE is any AE with a relationship to the study drug of possibly, probably, likely, or missing.

For partial AE and medication start dates:

- If the year is unknown, then do not impute the date but assign a missing value.
- If the year is known, but the month or month and day is unknown, then:
 - If the year matches the year of first dose date and the end date (if present) is after first dose date, then impute as the month and day of the first dose date.
 - Otherwise, assign 01 January.
- If the year and month are known, but the day is unknown, then:
 - If the month and year match the month and year of the first dose date, then impute as the day of the first dose date.
 - Otherwise, assign 01.

For partial AE and medication end dates:

- If the year is unknown, then do not impute the date but assign as missing value.
- If the year is known, but the month or month and day is unknown, then:

- If the year matches the year of the last date of the study (date of last contact if subject lost to follow-up; date of completion or early termination otherwise), then impute as the month and day of the last date of the study.
- Otherwise, assign 31 December.
- If the year and month are known, but the day is unknown, then:
 - If the month and year match the month and year of the last date of the study, then impute as the day of the last date of the study.
 - Otherwise, assign the last day of the month.

These conventions will be applied to AE and medication onset dates and times with the following precaution: if the missing date and time reflect the date and time of onset of an AE, the modified date and time will be constructed to match the first documented date/time post drug administration while preserving the order in which the AE was reported in the eCRF.

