8.2.2. Psoriasis Scalp Severity Index (PSSI)

The PSSI is used to measure the severity of psoriasis, combining the assessment of the severity of scalp lesions and the area of scalp affected into a single score ranging from 0 (no disease) to 72 (maximal disease). The PSSI score will be analyzed as follows:

- Change and percent change from baseline to Weeks 2, 4, 8, and 9 in the PSSI will be analyzed using descriptive summaries and an analysis of covariance (ANCOVA) with terms for country, baseline S-IGA category, and baseline B-IGA category, and baseline PSSI score as a covariate. Statistical comparisons between the treatment groups will be obtained using contrasts. The least-squares (LS) means, standard errors, 95% CIs, and *P* values will be presented.
- Frequencies and percentages of subjects achieving PSSI-50, PSSI-75, PSSI-90, and PSSI-100 will be presented by study week and treatment group. Additionally, these endpoints will be analyzed similar to the primary efficacy endpoint using a CMH test stratified by country, baseline S-IGA category, and baseline B-IGA category, on observed data. Only the PSSI-75 and PSSI-90 at Week 8 using the ITT population will be included in the testing strategy. Odds ratios and 95% CIs of the odds ratios will be provided. Additionally, the 95% Wilson CIs for proportion of successes in each treatment group will be presented.
- Time to achieving PSSI-50, PSSI-75, and PSSI-90 will be summarized using Kaplan-Meier methods and the difference between treatment groups evaluated using the log-rank statistic, and 95% CIs of the median for each treatment group will be presented. In addition, a Cox proportional hazards model that includes the stratification factors will be run and the hazard ratio and associated 95% Wald CIs will be presented. Time to achieving PSSI-50 using the ITT population will also be included in the testing strategy. Time to achieving PSSI-75 or PSSI-90 using the ITT population will not be included in the testing strategy, but will be considered as a supportive analysis.

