[1] PSSI-50 is populated with "Yes" when there is an achievement of a 50% reduction in PSSI total score from baseline; "No" otherwise.

[2] PSSI-75 is populated with "Yes" when there is an achievement of a 75% reduction in PSSI total score from baseline; "No" otherwise.

[3] PSSI-90 is populated with "Yes" when there is an achievement of a 90% reduction in PSSI total score from baseline; "No" otherwise.

[4] PSSI-100 is populated with "Yes" when there is an achievement of a 100% reduction in PSSI total score from baseline; "No" otherwise.

[5] 95% CI for "Yes" are obtained using Wilson method.

[6] The odds ratio, 95% CI, and P value are obtained from Cochran Mantel Haenszel test (stratified by country, baseline S-IGA score category, and baseline B-IGA score category) comparing roflumilast foam 0.3% to vehicle.

Reference Listings: 16.2.6.1, 16.2.6.2, 16.2.6.3

Table 14.2.3.4
Summary of Achievement of PSSI-50, PSSI-75, PSSI-90, and PSSI-100 by Study Visit
mITT Population

(Programming note: Same as table 14.2.3.3.)

Table 14.2.3.5
Time to Achievement of PSSI-50, PSSI-75, and PSSI-90
ITT Population

Variable Statistic	Roflumilast Foam 0.3% (N=XXX)	Vehicle (N=XXX)
Time to Achieve PSSI-50 (Days) [1]		
n	XXX	XXX
Events/Censors [2]	XX/XX	XX/XX
Mean (SD)	X.X (X.XX)	X.X (X.XX)
Median	X.X	X.X
Min, Max	X, XX	X, XX
Kaplan-Meier Estimate of Time to Achieve PSSI-50 (Days)		
Median (95% CI)	X.X (X.X, X.X)	X.X (X.X, X.X)
P value [3]	X.XXXX	
Cox Proportional Hazards Model [4]		
Hazard Ratio	X.XXX	
(95% Wald CI for Hazard Ratio)	(X.XXX, X.XXX)	

Repeat for “Time to Achieve PSSI-75 (Days) [5]” and “Time to Achieve PSSI-90 (Days) [6]”

Abbreviations: CI = confidence interval; NE = not estimable; PSSI = Psoriasis Scalp Severity Index; SD = standard deviation.
 Note: Subjects are summarized by planned treatment. Censored values are not included in the descriptive statistics. Only subjects who achieved PSSI-50, PSSI-75, or PSSI-90 are included in the relevant descriptive statistics.
 [1] PSSI-50 is achievement of 50% reduction in PSSI from baseline. Time to PSSI-50 is calculated as date of PSSI-50 achievement - Day 1 date + 1.
 [2] Subjects who did not achieve PSSI-50, PSSI-75, or PSSI-90 were censored at day of discontinuation or date lost to follow-up, whichever is earlier.
 [3] P value was obtained from the log rank test where roflumilast foam 0.3% was compared to vehicle.

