14.3. Planned Listing Shells

Listing 16.2.1.1
Subject Disposition
All Subjects

Subject ID	Randomized Treatment	Complete Study? [1] eCRF Derived	Did Subject Complete Study? [1] Derived	Date of Completion/ Early Termination (Study Day)	Date of Last Study Visit (Study Day)	Reason for Early Termination [2]	Cause of Death/ Date of Death	Early Termination Due to COVID-19 Disruption
XXXXXX	XXXXXX	Yes	Yes	DDMMYYYY (XX)	DDMMYYYY (XX)			
XXXXXX	XXXXXX	Yes	Yes	DDMMYYYY (XX)	DDMMYYYY (XX)			
XXXXXX	XXXXXX	Yes	Yes	DDMMYYYY (XX)	DDMMYYYY (XX)			
XXXXXX	XXXXXX	No	Yes	DDMMYYYY (XX)	DDMMYYYY (X)	XXXXXXXXXX: XXXXXXXXXX		
XXXXXX	XXXXXX	No	Yes	DDMMYYYY (XX)	DDMMYYYY (XX)	XXXXXX	XXXXXX/ DDMMYYYY	XXX

Abbreviations: COVID-19 = novel coronavirus disease-19; eCRF = electronic case report form.

Note: Study day is calculated relative to the date of first application of study drug.

[1] The derived completion status is based on a subject completing the Week 8 visit; this is what is used in the subject disposition summary. The eCRF completion status is based on what was recorded in the eCRF.

[2] Based on the eCRF.

Programming Note: If reason for early termination is Other, concatenate the specify text as follows: "Other: XXXXXXXXXXXX"; if reason for early termination is lost to follow-up, concatenate with date of last contact as follows: "Lost to follow-up; date of last contact: DDMMYYYY".

Listing 16.2.1.2
 Subject Visits
 All Subjects

Subject ID	Treatment Received	Was Visit Performed?	Visit	Visit Date (Study Day)	If Visit not Performed, COVID-19 Disruption Contributed to Missed Visit
XXXXXX	XXXXXX	Yes	XXXXXXXXXX	DDMMYYYY (XX)	
		Yes	XXXXXXXXXX	DDMMYYYY (XX)	
		Yes	XXXXXXXXXXXX	DDMMYYYY (XX)	
		No	XXXXXXXXXX		Yes
XXXXXX	XXXXXX	Yes	XXXXXXXXXX	DDMMYYYY (XX)	
		Yes	XXXXXXXXXX	DDMMYYYY (XX)	

Abbreviation: COVID-19 = novel coronavirus disease-19.

Note: Study day is calculated relative to the date of first application of study drug.

Listing 16.2.2.1
Inclusion and Exclusion Criteria
All Subjects

Subject ID	Was Subject Rescreened?	Subject Screen Failed due to COVID-19 Disruption	Randomized Treatment	Date/Time (Study Day) of:			All Inclusion Criteria Met? [1]	Any Exclusion Criteria Met? [2]
				Screening	Informed Consent	If Adolescent, Date of Written Assent		
XXXXXX	XX		XXXXXX	DDMMYYYY (-X)	DDMMYYYYY/hh:m m (-X)	Yes	No	
XXXXXX	XX	XX		DDMMYYYY	DDMMYYYY	No: 05, 13	No	
XXXXXX	XX	XX		DDMMYYYY	DDMMYYYYY/hh:m m	No: 02	No	
XXXXXX	XXX		XXXXXX	DDMMYYYY (-X)	DDMMYYYY	Yes	Yes: 02	

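### Time to PSSI-50, an alpha-controlled endpoint, has opposite censoring rules in SAP 6.1.7 and in its table shell, and neither rule censors at the last PSSI assessment

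*SAP*

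**What the plan says.** SAP 6.1.7 defines time to PSSI-50 in days from the Day 1 date and states: "Subjects not achieving PSSI-50 will be censored at day of study discontinuation or date lost to follow-up, whichever is later". The entries for PSSI-75, PSSI-90 and PASI-50 repeat that wording. For the three PSSI endpoints, 6.1.7 accepts times after Week 9, because COVID-19 site closures made some discontinuation visits very late.

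SAP 14.2, Table 14.2.3.5 shell, footnote [2], says non-achievers "were censored at day of discontinuation or date lost to follow-up, whichever is earlier". The PASI-50 shells (Tables 14.2.6.7 and 14.2.6.8) are built from this one and inherit the footnote.

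The endpoint is confirmatory. Under SAP 6.1.3, alpha 0.03 "will be used with a Holm testing procedure to test the 4 endpoints of time to success in PSSI-50" and three others, once S-IGA, B-IGA and PSSI-75 have succeeded. SAP 8.2.2 adds: "Time to achieving PSSI-50 using the ITT population will also be included in the testing strategy".

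Four other places bear on which dates exist:
- SAP 6.2 lists PSSI among the assessments that cannot be done remotely.
- Protocol 5.5 asks that a termination visit include the Week 9 procedures, which include PSSI.
- SAP 6.1.5 says: "Unscheduled, early termination, and/or repeated measurements will only be included if a scheduled measurement is not available" and it falls in the visit window; the Week 9 window has no upper limit.
- Listing 16.2.1.1 (SAP 14.3) has a completion or early termination date and adds a second: "if reason for early termination is lost to follow-up, concatenate with date of last contact as follows". SAP 6.1.8 instead treats the two as alternatives: "date of last contact if subject lost to follow-up; date of completion or early termination otherwise".

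**The concern.** There are two faults.

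First, the definition and the table that reports it give opposite rules, both in current SAP text, and nothing says which governs. They differ for any subject who has both a discontinuation date and a lost-to-follow-up date.

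Second, PSSI-50 status is known only when PSSI is scored. A subject last scored at Week 4 but censored at a later administrative or contact date stays in the Week 8 and Week 9 risk sets as if observed not to respond. The 'later' rule does this for a lost subject with no late on-site visit. Both rules do it when the only date held is a late discontinuation date. The 'earlier' rule does it when a phone contact follows the last PSSI. Neither rule names a date for a subject who completes without reaching PSSI-50.

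At stake are the p-value for this endpoint and, through Holm, the step that the other three endpoints face. The direction of any error depends on which arm loses more visits. The mITT repeat (Table 14.2.3.6) probes COVID-19 loss but is not the alpha-controlled test.

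**Working it through.** **Alpha.** The split is 0.03 + 0.02 = 0.05. Four endpoints share 0.03, so the Holm steps are 0.03/4 = 0.0075, 0.03/3 = 0.01, 0.03/2 = 0.015 and 0.03. The documents give no power figure for time to PSSI-50, so there is none to reproduce.

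**One subject.** Suppose PSSI is scored on Days 15, 29, 57 and 64 (schedule day + 1). A non-achiever has a last PSSI and last contact on Day 29, and discontinuation is recorded on Day 120.
- Later: censored Day 120; at risk on Days 57 and 64, unobserved at both.
- Earlier: censored Day 29; at risk at neither.
- Last PSSI: censored Day 29.

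If the last contact is instead a phone call on Day 60, 'earlier' gives Day 60 and the subject is wrongly at risk on Day 57.

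**Simulation (all rates and dates assumed).** Two-sided log-rank test, 200 active and 100 vehicle (the planned sizes), 20,000 trials per scenario. Cumulative PSSI-50 at Weeks 2/4/8/9 is 22/33/45/46% on vehicle, and 30/44/58/60% (smaller effect) or 35/50/65/67% (larger effect) on active. Loss is random within arm, and lost subjects miss the Week 8 and 9 PSSI. In the base case, last contact is Day 29, discontinuation is recorded on Days 90-150, and both dates are present. The base-case 'earlier' date is therefore also the last-PSSI date. Results are not conditioned on the preceding gates. The simulation standard error for power is at most 0.004.

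Power, later vs earlier:

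| Scenario | Loss 15% active / 5% vehicle | Loss 5% active / 15% vehicle |
|---|---|---|
| Smaller effect, 0.03 | 0.442 vs 0.526 | 0.605 vs 0.525 |
| Smaller effect, 0.0075 | 0.252 vs 0.324 | 0.395 vs 0.325 |
| Larger effect, 0.03 | 0.856 vs 0.899 | 0.927 vs 0.894 |
| Smaller effect, 0.03, half of lost subjects have a late PSSI | 0.447 vs 0.487 | 0.609 vs 0.574 |

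An 8,000-trial repeat of the base case gave 0.433 vs 0.516 and 0.600 vs 0.525 at 0.03. With equal 10% loss it gave 0.520 vs 0.524.

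Where the rules agree, or 'earlier' also misses (smaller effect, 0.03):
- Only a late discontinuation date held: both rules give 0.441 against 0.529 for last-PSSI censoring (15%/5%), and 0.595 against 0.520 (5%/15%).
- Last contact on Days 29-85: 'earlier' gives 0.483 against 0.526, and 0.562 against 0.521.

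**Type I error at nominal 0.03.** Under 'later' it is 0.028-0.035 at 5-15% loss. At 30%/10% or 10%/30% loss it is 0.039-0.047 (0.010-0.014 at nominal 0.0075). Last-PSSI censoring there gives 0.030-0.031 (0.007-0.008).

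**Second simulation, different assumptions.** 3,000 trials; true Week 9 PSSI-50 of 58.4% and 43.6%; exit 7-21 days after the last PSSI ('earlier' date) or on Days 66-119 ('later' date). With equal 10% loss the Kaplan-Meier estimates under 'later' fall to 56.1% and 41.6%, while rejection at 0.0075 is 36.0% against 37.2% for last PSSI. Equal loss thus biases the curves more than the test. With no effect and 10% active/30% vehicle loss, 'later' rejects 5.4% at nominal 3%, and last PSSI 2.9%.

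**The case against.** The strongest reply concerns size.

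- **Few subjects may carry both dates.** Last contact is added only for subjects lost to follow-up, one of ten discontinuation reasons in Table 14.1.1. If a third of losses are of that kind (assumed) and the rest leave on Day 29 with one date, the smaller-effect power at 0.03 is 0.495 vs 0.528 and 0.542 vs 0.515. The gap is about 3 points instead of 8. For the larger effect it is 0.879 vs 0.895 and 0.909 vs 0.897. This stands, but does not touch the case of a single late date without a PSSI.
- **The smaller effect exaggerates the gap.** Power near 50% is where a rule change shows most, and the test is reached only after three successes. If the S-IGA planning odds ratio carried over (32.2% vs 9.8%, about 4.4; 46% would become about 79%), power at 0.0075 is at least 0.996 under every rule. This is fair, but a PSSI-50 effect of that size is itself an assumption.
- **Late visits should include PSSI, and closures hit sites rather than arms.** Where PSSI is done at the late visit, the discontinuation day is the last PSSI date and the rules agree. With equal loss the test hardly moves. Both points stand. Neither rules out lost subjects without a late PSSI, or unequal loss.
- **Missing counts as nonresponse.** SAP 6.1.4.1 says this for responder analyses. It gives no censoring date, and 8.2.2 uses observed data for the PSSI responder rates.

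The textual conflict and the absence of a precedence rule are not answered.

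**Conclusion.** The concern holds. The two passages prescribe opposite censoring dates for an alpha-controlled test, and neither ties censoring to the last time PSSI was observed. Confidence is high for the conflict.

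The size is illustrative. The effect on the test ranges from nil (equal loss, a late PSSI for every lost subject, or a very large effect) to about 8 points of power in either direction (a 10-point loss imbalance, smaller effect, both dates for every lost subject). Type I error stays close to 0.03 at 5-15% loss under 'later' and exceeds it clearly only with strongly unequal, heavy loss.

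This is a gated secondary endpoint and the primary analysis is unaffected. The SAP should be corrected before unblinding, when the choice cannot be influenced by the result.

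**What to change.** Put one rule in SAP 6.1.7 and in footnote [2] of the Table 14.2.3.5 shell: a subject who does not achieve PSSI-50 is censored at the date of the last PSSI assessment. This also gives completers an explicit date. Apply it to PSSI-75 and PSSI-90, and use the last PASI assessment for PASI-50 and its shells.

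The stated choice to allow PSSI-50 times after Week 9 can remain. If the sponsor prefers to match the Day 68 cap set for PASI-50, align the day count first. If the Day 1 date is the first application (schedule Day 0), the end of the Week 9 window at 63 + 5 = 68 becomes 68 + 1 = Day 69, and the cap would drop an in-window visit. The censoring repair does not depend on this.

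The cost is SAP wording, one footnote and one derivation, with no new data. The trade-off is that lost subjects without a late PSSI leave the risk set earlier than under the present 6.1.7 text.
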